8.1 Number of Subjects Planned

Approximately 244 subjects will be randomized in this 3-month, parallel-group, bilateral, Investigator-masked study at 13 investigative sites in the US enrolling Chinese subjects.

8.2 Subject Inclusion Criteria

To be eligible for entry into the study, the subject must meet the following inclusion criteria:

1. Subject must be of legal age (at least 18 or as defined by state law) on the date the ICF is signed and have the capacity to provide voluntary informed consent.
2. Subject must be able to read, understand and provide written informed consent on the IRB approved ICF and provide authorization as appropriate for local privacy regulations.
3. Subject must have physiologically normal anterior segments not exhibiting clinically significant biomicroscopy findings (greater than Grade 1 and/or presence of infiltrates) and have clear central 6 mm corneas.
4. Subject must be an adapted wearer of soft contact lenses, wear a lens in each eye, and each lens must be of the same manufacture and brand.
5. Subject must have vision correctable through spherocylindrical refraction to 45 letters (0.04 logMAR) or better (distance, high contrast) in each eye. Visual acuity of 0.04 logMAR is the acuity where an individual subject would be given credit for reading logMAR 0.0 and logMAR 0.0 is equivalent to Chinese logarithmic visual acuity chart value of 5.0.
6. Subject must be myopic or hyperopic and require lens correction from +4.00 diopter (D) to -9.00 D in both eyes.
7. Subject must be a habitual wearer of toric soft contact lenses.
8. Subject must be able to be fit in both the Test and Control lenses in the listed parameters.
9. Subject have no active ocular disease or allergic conjunctivitis.
10. Subject must not be using any topical ocular medications.
11. Subject must agree to wear their study lenses on a daily wear basis for the duration of the study.
12. Subject must be willing and able to follow the visit schedule and follow instructions for use of the study products.

Written informed consent, enrollment in the study, or dispensing of study products cannot begin until the Investigator has received IRB approval to conduct the study. The Sponsor and IRB must approve any advertising used to recruit subjects prior to use of that advertising.

All consented subjects must be accounted for, whether they participate in the study or not. Bausch + Lomb will provide a Screening Log on which to enter information for each subject

who signs an ICF. All screened subjects must be entered onto the Screening Log, in the order in which they were consented, where they will be assigned a sequential subject identification (ID) number. Once a potential subject is consented and their initials are entered onto the Screening Log, the Investigator should proceed with Screening procedures.

Potential subjects are deemed either “Screen Pass” or “Screen Fail.” “Screen Fail” subjects have not met the study inclusion criteria or have met the exclusion criteria. “Screen Fail” subjects cannot be randomized. Subjects are considered enrolled when they have signed the ICF. The copy of their signed ICF and any information collected as part of screening (eg, source documents, etc.) must be kept in their medical records.

“Screen Pass” subjects have met all of the study inclusion criteria and have not met any of the exclusion criteria. Only “Screen Pass” subjects can be randomized to receive the study lenses.

Once a subject has signed the ICF, a subject is considered enrolled and must be accounted for at every visit until exited (completed, discontinued, or non-dispensed) from the study, even if they are not dispensed study materials.

8.3 Subject Exclusion Criteria

The subject is *not* eligible to participate in the study if the subject meets any of the following exclusion criteria:

1. Subject has worn gas permeable (GP) contact lenses within last 30 days or polymethylmethacrylate (PMMA) lenses within last 3 months.
2. Subject has systemic disease affecting ocular health.
3. Subject is using any systemic or topical medications that will affect ocular physiology or lens performance.
4. Subject has an active ocular disease (for example but not limited to papillary conjunctivitis, any conjunctivitis: viral, bacterial, allergic), any corneal infiltrative response or are using any ocular medications.
5. Subject has any “Present” finding during the slit lamp examination that, in the Investigator’s judgment, interferes with contact lens wear.
6. Subject has any scar or neovascularization within the central 6 mm of the cornea. Minor peripheral corneal scarring (that does not extend into the central 6 mm of the cornea), that in the Investigator’s judgment, does not interfere with contact lens wear, are eligible for this study.
7. Subject has anisometropia (spherical equivalent) of greater than 2.00 D based on spherocylindrical refraction.
8. Subject is aphakic.
9. Subject is amblyopic.

10. Subject has had any corneal surgery (eg, refractive surgery).
11. Subject is participating in a conflicting study (or actively participating within another active cohort of this study).
12. Subject has participated in any drug or device clinical investigation (within 14 days) prior to entry into this study and/or during the period of study participation.
13. Subject is a woman of childbearing potential if one of the following: pregnant, plans to become pregnant during study or is breast feeding.
14. Subject meets any of the following criteria:
 - Ophthalmologist, OD, Optician, Ophthalmologist's Assistant/Technician
 - employee of a market research firm
 - employee of manufacturer of contact lens or contact lens care products
 - employee of the investigational site
15. Subject wears monovision or multifocal contact lenses.
16. Subject is considered by the Investigator to not be a suitable candidate for participation.

If a subject meets all the inclusion criteria and does not exhibit any of the exclusion criteria, the subject is eligible to be enrolled into the study. Ineligible subjects MUST NOT be enrolled in this study and are considered a “Screen Fail”. Any subject enrolled in the study who later is found to have not met the eligibility criteria at entry will be discontinued.

Note: Any exceptions to the Inclusion and Exclusion criteria must be cleared by the Sponsor.

8.4 Subject Withdrawal Criteria

8.4.1 List of Treatment Withdrawal Criteria

A subject MUST be discontinued prior to the final study visit for any of the following reasons:

- voluntary withdrawal
- death
- Investigator decision that it is not in the best medical interest of the subject to continue participation in the investigation
- ineligible at the Screening Visit - does not meet the eligibility criteria in the protocol
- inability to maintain recommended wearing schedule
- continued failure to follow subject instructions
- misses more than 1 Follow-up Visit, not including the 3-Month Visit

- lack of motivation
- lost to follow-up (see [Section 8.4.3](#))
- instillation of non-medically indicated solution not specified in the protocol
- other eye is discontinued
- becomes pregnant during the study
- 3-month follow-up visit is conducted prior to Day 92

Prior to discontinuing a subject, every effort should be made to contact the subject, schedule a final study visit, obtain as much follow-up data as possible, and to retrieve all study materials. Adverse events will be followed as described in [Section 11.5.8](#). Subject discontinuations will be documented clearly on the source document and applicable eCRF. The Investigator should indicate the PRIMARY (one) reason that the subject was discontinued for each eye. Subjects that are discontinued from the study following randomization will not be replaced.

8.4.2 Reasons for Treatment Withdrawal

A subject MAY be discontinued (at the discretion of the Investigator, the Sponsor, and/or the IRB) prior to the final study visit for a variety of reasons, including, but not limited to:

- an AE occurring during the course of the study, which precludes continued treatment or follow-up
- persistent slit lamp findings (must be reported to the Sponsor within 24 hours) of the following grades:
 - Moderate
 - Severe
- persistent study-related symptoms/complaints
- unacceptable distance lens VA, lens centration, lens movement, or unacceptable lens rotation

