- g. Discuss the diary with instructions to complete on a weekly basis. Subjects will be provided with a reminder at every visit to complete the diary to capture wear experience on a weekly basis until they exit the study.
- h. If the subject is discontinued or exited at this visit, complete the Exit Visit eCRF.
- i. Re-emphasize the exclusion criterion stating that if the subject is a female of child bearing potential and is pregnant and or breast feeding, she is ineligible to be a part of the study.

11.1.3 1-Week, 1-Month, and 3-Month Follow-up Visits

- a. If this is an Exit Visit, indicate that on the eCRF and, in addition to completing the appropriate Follow-Up Visit Form, complete the Exit Visit Form. If a subject misses the scheduled follow-up visit and cannot be seen prior to the start of the visit window for the next scheduled follow-up visit, then the visit is considered missed and it should be recorded as a missed visit in the applicable eCRF.
- b. Collect/assess all AEs, including serious or significant non-serious AEs.
- c. If the subject did not wear lenses to the visit, the subject can use a pair from the 10 lenses per eye stored in the office to complete the assessment.
- d. Collect Symptoms/Complaints information using the Symptoms/Complaints Rating Scales in [Appendix A](#) and record them in the source documentation and eCRF.
- e. Evaluate the lenses (while on eye) and record the following assessments in the source documentation and eCRF:
 - distance high contract lens VA
 - over-refraction and distance VA
 - lens wettability
 - lens centration
 - lens movement

- lens rotation
- lens deposits

For each eye, compare the high contrast distance contact lens VA from each respective / current visit (1-Week, 1-Month, 3-Month Follow-up Visits) to the high contrast distance contact lens VA obtained at the Dispensing Visit. If the VA has decreased by 10 letters (0.2 logMAR) or more, record in the subject's source document and explain.

- f. Perform a slit lamp examination (remove the lenses if the subject wore lenses to the visit) and record the following assessments in the source documentation and the eCRF. Record all slit lamp findings and, at a minimum, sketch the following in the subject's source document:
 - any ungraded finding marked as "PRESENT"
 - any new corneal scars
 - any neovascularization within the central 6 mm of the cornea
 - any corneal staining

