12.2.2 Per Protocol Population

The PP Population will include all randomized subjects without major protocol deviations who complete the study through Visit 3 (Days 6 - 10). Major protocol deviations affecting only one eye will result in the exclusion of both eyes from eye level summaries.

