12.3.2 Primary Effectiveness Analysis

At the 1-Week Follow-up Visit, subjects with non-missing logMAR acuities 0.04 or better in both eyes will be classified as “0.04 or Better.” Subjects with at least one logMAR acuity > 0.04 at the visit will be classified as “Worse than 0.04.” Subjects with at least one missing value at the visit will not be classified and their classification value will be assigned as missing. Visual acuity of 0.04 logMAR is the acuity where an individual subject would be given credit for reading logMAR 0.0 and logMAR 0.0 is equivalent to Chinese logarithmic visual acuity chart value of 5.0.

The summaries and analyses of the primary effectiveness endpoint will be at the subject level.

Use of the ITT Population and imputation of missing values are not conservative practices in non-inferiority analyses. Consequently, the PP Population will be used for the primary analysis without imputation of missing data.

Primary Non-Inferiority Analysis with the Per Protocol Population

VA Effectiveness will be summarized categorically (0.04 or Better, Worse than 0.04) by treatment group at the 1-Week Follow-up Visit for the Per Protocol (PP) Population in a table. Missing data will not be imputed for this primary analysis of the PP Population. The denominator for percentages will be the number of non-missing values.

The difference between treatment groups (Test minus Control) in the proportion of subjects classified as “0.04 or Better” will be estimated. An asymptotic Wald non-inferiority test (without continuity correction; using the sample variance; alpha risk = 0.025) and the associated two-sided 95% confidence interval will be used to test the statistical hypothesis. The difference between treatment groups (in percentage units), the asymptotic standard error for the difference (in percentage units), the associated Z value, the p-value for the non-inferiority test, and a two-sided 95% confidence interval (in percentage units) around the difference will be presented. [REDACTED]

Sensitivity Analysis Using the ITT Population

VA Effectiveness will be summarized categorically (0.04 or Better, Worse than 0.04) by treatment group at the 1-Week follow-up visit for the ITT Population in a table. The denominator for percentages will be the number of non-missing values. Missing data will not be imputed for this categorical summary.

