If there are no missing lens VA data at the 1-Week follow-up visit for ITT subjects, then the following will be completed.

- The difference between treatment groups (Test minus Control) in the proportion of subjects classified as “0.04 or Better” will be estimated.

If there are missing lens VA data for ITT subjects at the 1-Week follow-up visit then missing data will be imputed as follows prior to hypothesis testing.

- The difference between treatment groups (Test minus Control) in the proportion of subjects classified as “0.04 or Better” and the asymptotic standard error will be estimated by imputation.
- An estimated difference between treatment groups and two-sided asymptotic Wald 95% confidence interval around the difference will be constructed via combination of the proportion differences and standard errors from the imputations.
- If all of the imputations result in the same estimated difference and confidence interval, then the results of a single imputation may be used.

The estimated difference between treatment groups (Test minus Control) in the percentage of subjects classified as “0.04 or Better” will be presented along with the two-sided asymptotic Wald 95% confidence interval around the difference.

Evaluation of Sensitivity to Missing Data

As an evaluation of sensitivity to missing VA Effectiveness data, a best-case analysis, worst-case analysis, and tipping point analysis will be completed for the ITT Population (Xu et al, 2009). If there are no missing ITT Population data then these analyses will not be completed.

Evaluation of the Influence of Site on the Treatment Effect

VA Effectiveness will be summarized categorically (0.04 or Better, Worse than 0.04) by treatment group and site for the ITT Population in a table. This will be a subject level summary. The denominator for percentages will be the number of non-missing values. Missing data will not be imputed.

A Breslow-Day test for homogeneity of odds ratios will be used to evaluate the consistency of the treatment effect among the sites. If the p-value from this test is less than 0.05 then the difference between sites will be considered to be statistically significant.

Evaluation of the Influences of Age, Sex, and Descent on the Treatment Effect

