12.6 Protocol Deviations

The following protocol deviations will be classified as major deviations when reported in the case report forms.

- Ineligibility
- Non-dispensed subjects
- Misrandomization
- Dispensing or use of the incorrect lens type
- Dispensing of the incorrect lens power, defined as a discrepancy greater than 0.25D in sphere, cylinder, or spherical equivalent
- Non-compliance with the recommended wearing schedule, such as
 - wearing lenses less than 80% of the recommended time, or
 - wearing a lens for multiple days

- Use of medications that could potentially affect ocular physiology or lens performance
- Failure to comply with the procedures used to assess primary effectiveness endpoints, such as missing the assessment or failing to complete the procedure in accordance with the instructions provided by site personnel.

Additional major categories may be added prior to unmasking. Major deviations will be provided in a listing.

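### A subject withdrawn for unacceptable lens vision before the 1-Week visit drops out of the Per Protocol primary test instead of counting as a failure; the effect is probably small and cheap to close

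*Combined protocol and SAP*

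**What the plan says.** - **Withdrawal.** Section 8.4.2 lists, among reasons for which a subject may be withdrawn, "unacceptable distance lens VA, lens centration, lens movement, or unacceptable lens rotation". The decision is "at the discretion of the Investigator, the Sponsor, and/or the IRB". No acuity threshold is given.
- **Timing.** Table 1 first schedules study-lens acuity at the Dispensing Visit, after randomization. Section 11.1.2 foresees that a subject may leave there: "If the subject is discontinued or exited at this visit, complete the Exit Visit eCRF". Section 11.1.5 also allows exit at an Unscheduled Visit.
- **Endpoint.** Success is lens-corrected logMAR acuity of 0.04 or better in both eyes at the 1-Week visit (11.4.1).
- **Analysis set.** Section 12.2.2 limits the Per Protocol Population to subjects without major deviations "who complete the study through Visit 3 (Days 6 - 10").
- **Missing values.** Section 12.3.2 (and the synopsis) adds: "Subjects with at least one missing value at the visit will not be classified and their classification value will be assigned as missing". The primary analysis uses no imputation and a denominator of non-missing values. The stated ground is that ITT analysis and imputation are not conservative for non-inferiority.
- **Deviations.** Section 12.6 lists as major "Failure to comply with the procedures used to assess primary effectiveness endpoints, such as missing the assessment".
- **Sensitivity.** Section 12.3.2 plans an imputed ITT analysis and, if data are missing, states that a best-case analysis, "worst-case analysis, and tipping point analysis will be completed for the ITT Population".

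**The concern.** A subject taken off study lenses because vision through them was judged inadequate has had an outcome close to what the trial measures. The plan treats that subject as if nothing had been learned. This is an exclusion related to outcome, and it sits in the analysis chosen for being conservative.

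The direction depends on the truth. With equal lenses and equal handling, both success rates rise by the same amount and the difference is unaffected. If Test is worse, Test has more failures available to remove, the observed difference shrinks towards zero, and the non-inferiority test passes too often. That second case is the one that the one-sided 2.5% limit is meant to control. Few failures are expected (7.5% of 109 is about 8 per arm at the planning rate), so losing two or three can move the confidence limit.

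**Working it through.** **1. The plan's own figure.** Inputs from 12.1.1: 92.5% in both arms, margin 10 points, one-sided alpha 0.025, power 80%.

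n = 2 × 0.925 × 0.075 × (1.960 + 0.842)² / 0.10² = 108.9, so 109 per arm. This reproduces the plan. Section 12.1.2 then gives 109/0.9 = 121.1, so 122 per arm and 244 in total.

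**2. The path through the text.** A subject is dispensed lenses, has lens acuity measured, and is withdrawn for that acuity before Day 6–10. Visit 3 is not completed, so 12.2.2 removes the subject. That rule is enough. The missing-value rule in 12.3.2 would give the same result but is not reached within the Per Protocol set. Table 1 has no study-lens acuity at the Exit Visit, and lens acuity from a Dispensing or Unscheduled Visit does not feed the endpoint. A subject who exits at the 1-Week visit is not affected, because 11.1.3 has the follow-up form completed as well as the exit form.

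**3. Size.** The documents give no rate for such exits. Assume that a share q of would-be failures is removed, the same share in each arm. With true success p and n = 109:

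- remaining subjects: n′ = n(1 − (1 − p)q)
- apparent success: p′ = p / (1 − (1 − p)q)
- SE = √[p′_T(1 − p′_T)/n′_T + p′_C(1 − p′_C)/n′_C]
- P(declare non-inferior) = Φ((p′_T − p′_C + 0.10)/SE − 1.96)

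Set p_T = 0.825 and p_C = 0.925, exactly on the margin, where the nominal answer is 2.5%.

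| q | Expected removed, Test v Control | Expected difference (points) | P(declare non-inferior) |
|---|---|---|---|
| 0 | 0 v 0 | −10.0 | 2.5% |
| 2% | 0.4 v 0.2 | −9.8 | 2.7% |
| 5% | 1.0 v 0.4 | −9.6 | 3.1% |
| 10% | 1.9 v 0.8 | −9.2 | 3.7% |
| 20% | 3.8 v 1.6 | −8.4 | 5.7% |

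Worked line, q = 0.10:

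- Test keeps 1 − 0.175 × 0.10 = 0.9825, so p′_T = 0.825/0.9825 = 0.8397 and n′_T = 107.1.
- Control keeps 0.9925, so p′_C = 0.9320 and n′_C = 108.2.
- The difference is −9.23 points and the SE 4.29 points. Φ(0.77/4.29 − 1.96) is about 3.7%.

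With both arms at 92.5%, p′_T = p′_C at every q and the difference stays 0.

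**4. Simulation (2,000,000 trials).** The Wald test alone gives 3.0% at q = 0. As planned it gives 3.7%, 4.5% and 6.9% at q = 5%, 10% and 20%. With removed subjects counted as failures it is 3.0% at every q, so the proposed rule removes the added error.

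**5. One illustrative data set.** 99/109 v 104/109 gives −4.6 points, lower limit −11.3: non-inferiority not shown. Remove 20% of the failures in each arm (2 of 10 Test, 1 of 5 Control). Then 99/107 v 104/108 gives −3.8 points, lower limit −9.9: shown. The example uses the highest q in the table and only just crosses the margin.

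**The case against.** **Such exits should be few.** The window runs only from dispensing to Day 6–10. Entry requires best-corrected acuity of 0.04 or better in each eye (8.2), and the Appendix C guides ask for satisfactory or acceptable vision before dispensing. If dispensing acuity is five or more letters below spectacle acuity, 11.1.2 asks for an explanation, not withdrawal. Section 8.4.1 asks sites to try to obtain a final visit first. This stands, and it makes the 2% and 5% rows more plausible than the 20% row. At 5% the added error (0.6 points) is about the size of the Wald test's own excess in the simulation (0.5 points).

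**The effect would be visible.** The ITT worst-case and tipping-point analyses treat missing outcomes adversely, and 12.4 reports the main reason for stopping. This also stands, but those analyses make no stated use of the withdrawal reason and do not decide the primary test.

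**Stronger readings that the documents do not support.**

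- A reader might infer that the withdrawal reason is the endpoint itself, so that a known failure is discarded. Section 8.4.2 sets no threshold, and dispensing acuity is taken after as little as 3 minutes on the eye. A subject at 0.06 might be judged acceptable, and one at 0.02 with fluctuating vision might not.
- A reader might count three separate rules that remove the subject. The Visit 3 completion rule does the work, and applying the 12.6 item to an authorised withdrawal is an interpretation.
- A reader might assume exits in Test only. With Control 113/122, four Test exits would give a lower limit of −6.9 points if excluded (109/118) and −10.5 if counted as failures (109/122). Nothing in the documents suggests a one-sided pattern, so this is not the basis for the size given here.

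**Conclusion.** The gap is real but modest. A withdrawal for unacceptable distance lens acuity between dispensing and the 1-Week measurement leaves the primary analysis through 12.2.2, and nothing in the plan counts it against the lens.

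There is no bias in the difference if the lenses are equal and the same share of failures is removed in each arm. If Test sits on the 10-point margin, the false-positive rate rises from 2.5% to about 2.7–3.1% when 2–5% of failures are removed, and to 5.7% only when one failure in five is. These figures rest on an assumed equal removal share and on 109 analysed per arm. They do not show that the trial's error rate will double. The change is worth making because it is inexpensive and keeps the Per Protocol analysis in line with the conservative aim stated in 12.3.2.

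**What to change.** Before unmasking, add to 12.2.2, 12.3.2 and the synopsis:

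> A dispensed subject discontinued before a 1-Week lens VA is recorded, with unacceptable distance lens VA as the primary reason in either eye, is classified as Worse than 0.04 and stays in the Per Protocol Population if there is no other major deviation; the resulting missed assessment does not count as one.

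The either-eye wording is needed because of 8.4.1: "The Investigator should indicate the PRIMARY (one) reason that the subject was discontinued for each eye". The fellow eye may carry only the reason that the other eye was discontinued.

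Report these subjects by arm with their last recorded lens acuity. Present the analysis with them excluded as a sensitivity analysis.

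**Cost.** A few sentences and no new data: the per-eye reason and the dispensing lens acuity are already collected. Success rates may be slightly less favourable. The rule is also a single-value imputation in an analysis that the plan describes as without imputation. A few classifications would rest on a discretionary reason code, in a trial where subjects are unmasked, and not on a measured 1-Week acuity. The sensitivity analysis lets readers see how much depends on that.
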